7.1 Adverse events

An adverse event (AE) is any untoward medical occurrence (i.e., any unfavorable and unintended sign [including abnormal laboratory findings], symptom or disease) in a subject or clinical investigation subject *after providing written informed consent* for participation in the study. Therefore, an AE may or may not be temporally or causally associated with the use of a medicinal (investigational) product.

The occurrence of adverse events should be sought by non-directive questioning of the patient at each visit during the study. Adverse events also may be detected when they are volunteered by the patient during or between visits, or through physical examination, laboratory tests, or other assessments.

Abnormal laboratory values or test results constitute adverse events only if they fulfill at least one of the following criteria:

- they induce clinical signs or symptoms,
- they are considered clinically significant,
- they require therapy.

Clinically significant abnormal laboratory values or test results should be identified through a review of values outside of normal ranges/clinically notable ranges, significant changes from baseline or the previous visit, or values that are considered non-typical in a patient with underlying disease. Investigators have the responsibility for managing the safety of individual patient and identifying adverse events. Alert ranges for labs and other test abnormalities are included in [Appendix 1](#).

Adverse events should be recorded in the Adverse Events CRF under the signs, symptoms or diagnosis associated with them accompanied by the following information.

- the severity grade
 - mild: usually transient in nature and generally not interfering with normal activities
 - moderate: sufficiently discomforting to interfere with normal activities
 - severe: prevents normal activities
- its relationship to the investigational treatment (no/yes)
- its duration (start and end dates) or if the event is ongoing an outcome of not recovered/not resolved should be reported.
- whether it constitutes a serious adverse event (SAE)
- action taken regarding the investigational treatment
- whether other medication or therapies have been taken (concomitant medication/non-drug therapy)
- its outcome (not recovered/not resolved; recovered/resolved; recovering/resolving, recovered/resolved with sequelae; fatal; or unknown)

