7.3 Liver safety monitoring

To ensure patient safety and enhance reliability in determining the hepatotoxic potential of an investigational drug, a standardized process for identification, monitoring and evaluation of liver events has to be followed.

Liver events are divided into two categories:

- Liver events of special interest, which consist of liver function test (LFT) elevations.
- Medically significant liver events that are considered as serious adverse events and consist of marked elevations of LFTs and / or pre-specified adverse events.

Please refer to [Table 14-1](#) in [Appendix 2](#) for complete definitions of liver events.

Any liver event that meets the criteria for “**medically significant**” event, as outlined in [Table 14-1](#) of [Appendix 2](#), should follow the **standard procedures for SAE reporting** as described in [Section 7.2](#).

Every liver event as defined in [Table 14-1](#) of [Appendix 2](#) should be followed up by the investigator or designated personal at the trial site as summarized below.

- Repeat the LFT to confirm elevation as appropriate.
- Discontinue the investigational drug if appropriate.
- Hospitalize the patient if appropriate.
- Assess the causality of the liver event via exclusion of alternative causes (e.g., disease, co-mediations).
- An investigation of the liver event needs to be followed until resolution.

These investigations can include serology tests, imaging and pathology assessments, hepatology consultancy, based on the investigator's discretion. All follow-up information and the procedures performed should be recorded on appropriate CRF pages, including the liver event overview CRF pages.

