9.5.2 Safety variables

Vital signs

Summary statistics of vital signs and changes from baseline will be provided by visit and cohort. Clinically notable vital signs will be listed and absolute and relative frequencies will be presented by visit and cohort.

Height, weight and waist

Summary statistics will be provided for height, weight, waist and derived BMI (calculated from body weight and height) by visit and cohort including changes from baseline.

Hematology, clinical chemistry, urinalysis, hsCRP

Summary statistics of raw data and absolute and changes from baseline will be provided for laboratory data by visit and cohort.

Patients with values above (H) or below (L) notable criteria (see [Appendix 1](#)) will be listed and absolute and relative frequencies will be presented by visit and cohort. Laboratory values will be presented for each subject in a data listing with an indication of whether the value is above (H) or below (L) the normal reference range.

Laboratory data will also be summarized by presenting shift tables for each laboratory parameter showing the number and percentage of subjects in each cohort with the most extreme post-baseline value that falls outside normal ranges by the classification of value at baseline (H/N/L).

Adverse Events

A summary table of AEs will be produced by cohort specifying the number of total events and the absolute and relative frequency of patients with AEs. The absolute and relative frequency of patients with study drug related AEs, severe AEs, SAEs, AEs with an outcome of death, AEs leading to discontinuation of treatment will be also reported.

AEs will be tabulated also by System Organ Class, Preferred Term.

SAEs will be summarized as well.

All study drug related AEs, AEs with an outcome of death, AEs leading to discontinuation of treatment will be listed.

The above reported analysis will focus on treatment emergent adverse events. A treatment-emergent adverse event is defined as any adverse event that develops after initiation of the study treatments or any event already present that worsens following exposure to the study treatment. Non-treatment emergent adverse events will be listed separately.

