1.2 Study objectives and endpoints

Table 1.2-1 **Objectives and related endpoints**

Objective	Endpoint
Primary objective	
To evaluate the clinical response in Cw6- negative and Cw6-positive patients treated with secukinumab 300 mg with respect to the Psoriasis Area Severity Index (PASI) 90 response rate after 16 weeks, and	PASI 90 response after 16 weeks of treatment, defined as the achievement of \geq 90% improvement (reduction) in PASI score after 16 weeks of treatment compared to baseline and thereafter for

thereafter for up to 72 weeks.	up to 72 weeks.			
Secondary objective				
To compare the proportion of responders to PASI 50/75/90/100 between cohorts at each time point.	Proportion of responders to PASI 50/75/90/100 at each time point.			
To compare the mean changes vs baseline in the Investigator's Global assessment (IGA) mod 2011 between cohorts at each time point.	Change from baseline in IGA mod 2011 between Cw6-negative and Cw6-positive at each time point.			
To compare time to reach PASI 90 between cohorts.	Time to PASI 90 response between Cw6- negative and Cw6-positive.			
To compare time to reach PASI 75 between cohorts.	Time to PASI 75 response between Cw6- negative and Cw6-positive.			
To evaluate the quality of life by means of the Dermatology Life Quality Index (DLQI) in all patients at each time point.	Change from baseline in DLQI at each time point.			
To evaluate anxiety and depression using the Hospital Anxiety and Depression Scale (HADS) in all patients at each time point	Change from baseline in HADS at each time point.			
To evaluate the correlation between HADS and PASI in all patients.	Correlation coefficient between HADS and PASI.			
To evaluate changes from baseline in weight, BMI and waist in all patients at each time point.	Change from baseline in weight, BMI and waist at each time point.			
To compare safety and tolerability between cohorts during the 24 weeks, and then during the whole study period.	Overall safety, as measured by frequency and severity of adverse events and changes in laboratory, vital signs, ECG values and chest X-ray from values baseline.			
To evaluate the amount of resources used during the study in comparison with the 6 months prior to the beginning of the study.	Health resources use will be conducted considering the comorbidities (such as anxiety and depression), PsO medical history, concomitant medication and adverse event.			

2 Statistical methods

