2.8.1 Adverse events (AEs)

A summary table of AEs will be produced by cohort specifying the number of total events and the absolute and relative frequency of patients with AEs. All AEs which occur on or after the first dose of study treatment and on or before last dose of treatment will be considered as treatment emergent and remaining will be considered as non-treatment emergent. AEs which occur till last visit date of E0 will be reported under Core phase and which start after E0 visit will be reported under Extension phase. The detailed treatment emergent rules for AE reporting by phases are mentioned below:

Core phase

AEs occurring on or after first dose date and

- a) on or before the last visit date till E0, if patient discontinued the study
- b) on or before the last dose date till E0, if patient completed the study

Extension phase

- 1) Patient entered and dosed in extension
- 2) AEs occurring on or after first dose in extension and
 - a) on or before last visit date, if patient discontinued the Extension phase study
 - b) on or before last dose date, if patient completed the Extension phase study

Overall:

AEs occurring on or after first dose date and

- a) on or before last visit date if patient discontinued the Core or Extension phase study
- b) on or before last dose date if patient completed the study

Note: In addition to that, if last visit date is missing and last dose is after the non-missing last visit date, then treatment emergent flag will be considered till the last dose date.

The absolute and relative frequency of patients with study drug related AEs, SAEs, AEs with an outcome of death (if data is sufficient), AEs leading to discontinuation of treatment will be also reported by cohort and overall. Proportion and 95% CI will be calculated using exact binomial method. Differences between cohorts will be assessed by means of a logistic model

with factors (time of exposure, age at baseline (tertiles), sex, number of comorbidities (General and PsA), BMI class). Tertiles will be calculated from SAS using PROC Univariate of age at baseline.

AEs will be tabulated also by System Organ Class, Preferred Term. SAEs will be summarized as well. All study drug related AEs, AEs with an outcome of death, AEs leading to discontinuation of treatment will be listed. The above reported analysis will focus on treatment emergent adverse events.

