2.8.1.1 Adverse events of special interest / grouping of AEs

Neutropenia and candida infection will be considered as adverse events of special interest.

Adverse events of special interest will be summarized by cohort and overall divided by study phase on safety set and also will be listed separately. The below events from RMP will also be summarized, if possible. Differences between cohort will be assessed by means of a logistic model with factors (time of exposure, age at baseline (tertiles), gender, total number of comorbidities, BMI class). Tertiles will be calculated from SAS using PROC Univariate of age at baseline. If identifying the below SI is difficult, all RMP related events will be summarized.

Differences between cohorts on total number of events for each group of events (if possible) reported in the RMP will be analyzed by means of a Poisson regression model adjusting per time of exposure, age at baseline (tertile), gender, BMI class and total number of comorbidities according to the table below.

Event of special in	Comorbidities to	
Potential Risk	SMQ or SOC or HLT or PT (MedDRA Version 20.0)	take into account in the model
Infections and infestations	SOC: Infections and infestations	Diabetes (every form) (Y/N)
		Previous biologic and systemic therapy (yes vs no)
Neutropenia	PT: Agranulocytosis	

The total number of comorbidities for RMP related table will be defined by presence of at least one of the comorbidities mentioned below.

	Autoimmune neutropenia Band neutrophil count decreased Band neutrophil percentage decreased Febrile neutropenia Granulocyte count decreased Granulocytes maturation arrest Granulocytopenia Granulocytopenia neonatal Idiopathic neutropenia Leukopenia Metamyelocyte count decreased Myeloblast count decreased Myeloblast count decreased Neutropenia Neutropenia neonatal Neutropenic colitis Neutropenic colitis Neutropenic sepsis Neutrophil count decreased Neutrophil percentage decreased Pure white cell aplasia White blood cell count decreased	previous biologic therapy (yes vs no)
Malignant or unspecified tumours	SMQ: Malignant or unspecified tumours	SOC: "Neoplasms benign, malignant and unspecified"

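### SAP 2.8.1 drops, without declaring it, the severe-AE summary that protocol 9.5.2 requires; AEs with no start year also default to non-treatment-emergent

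*SAP*

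**What the plan says.** **Severity.** Protocol 9.5.2 lists the AE categories to be tabulated: "The absolute and relative frequency of patients with study drug related AEs, severe AEs, SAEs, AEs with an outcome of death", followed by AEs leading to discontinuation. The matching sentence in SAP 2.8.1 reads: "The absolute and relative frequency of patients with study drug related AEs, SAEs, AEs with an outcome of death (if data is sufficient", followed again by discontinuations. SAP Table 1.2-1 describes the safety endpoint as "Overall safety, as measured by frequency and severity of adverse events", together with laboratory and other changes. Protocol 7.1 has the investigator grade each AE on three levels, the top one being "severe: prevents normal activities". Seriousness is recorded as a separate item.

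**Dates.** SAP 2.8.1 first defines emergence by a date window from first to last dose. AEs inside it are "considered as treatment emergent and remaining will be considered as non-treatment emergent". Rules by phase then refine the upper limit of the window. Later in the same section comes a second definition: an AE that begins after treatment starts, or an existing one that worsens, with no upper limit. Non-emergent AEs are only listed. SAP 5.1.1 does not impute missing start dates, and its matrix shows no convention in every column when the year is missing.

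**Liver.** Protocol 7.3 defines two categories of liver event, the first being "Liver events of special interest, which consist of liver function test (LFT) elevations". Findings are recorded on dedicated pages, "including the liver event overview CRF pages". SAP 2.8.1.1 says: "Neutropenia and candida infection will be considered as adverse events of special interest". It adds groups of events from the risk management plan, of which the only hepatic one is hepatitis B reactivation.

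**The concern.** Comparing safety and tolerability between the Cw6 cohorts is a stated secondary objective in both documents. If the SAP is programmed as written, the AE output shows how many patients had events and how many had serious ones, but not how many had severe ones. Severe and serious are different attributes, so the SAE row cannot stand in for the missing one.

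The date rule matters for a different reason. An AE of unknown onset would be removed from the emergent tables by default, which is the less cautious direction for a safety summary.

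The liver events raise a question of completeness: a category that the protocol singles out for special follow-up has no summary of its own.

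**Working it through.** No sample size, power or rate is involved, so the check is a comparison of texts.

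**1. Severe AEs**

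| Category | Protocol 9.5.2 | SAP 2.8.1 |
|---|---|---|
| Drug-related AEs | yes | yes |
| Severe AEs | yes | absent |
| SAEs | yes | yes |
| Fatal AEs | yes | yes, if data suffice |
| AEs leading to discontinuation | yes | yes |

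Nothing else in the SAP fills the gap. The breakdown by organ class and preferred term is not split by grade. The Poisson models cover total AEs, SAEs and AEs of special interest. Section 5.2, on coding and grading, is marked not applicable. Section 4 has entries for 2.8.1 (the logistic and Poisson comparisons), but none mentions severity.

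**2. AEs without a start year**

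Take an AE that is ongoing. Under SAP 5.1.1 its start reference is the treatment start date.

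- *Year known and equal to the treatment year, month missing:* rule (B) gives reference + 1 day, that is, treatment start + 1 day. This falls inside the window, so the AE is emergent and tabulated.
- *Year missing:* no convention, so no date. The AE cannot be shown to start on or after first dose, falls into the remainder and is only listed.

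The same kind of event is therefore handled in opposite ways depending on whether the year was recorded. The concomitant-medication matrix in SAP 5.1.2 does assign a convention when the year is missing, so the gap is specific to AEs. SAP 2.1.1.5 also allocates AEs to core or extension by start date. For a patient who entered the extension, such an AE therefore has no phase either.

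**3. Liver events** (multiples of ULN)

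| Test | Protocol Appendix 1 | SAP Table 2.8.3 | Protocol Table 14-1, special-interest tier |
|---|---|---|---|
| ALT/AST | >3 | >3 | >3 |
| Total bilirubin | >2 | >2 | >1.5 |
| ALP | >2.5 | >2.5 | >2 |

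The SAP limits equal those of Appendix 1, which is where protocol 9.5.2 sends the analyst for notable values. The bands that meet Table 14-1 but no notable limit (bilirubin >1.5 to 2, ALP >2 to 2.5) lie between two appendices of the protocol itself. The medically significant tier of Table 14-1, including potential Hy's law cases, is reported as SAEs and so reaches the SAE summaries. What no output shows is these events grouped by Table 14-1 category. The notable-value tables take one test at a time and the shift tables use only high, normal and low, whereas a potential Hy's law case needs ALT/AST, bilirubin and ALP read together.

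**The case against.** On severity, the best defence is that the SAP introduction ties the analysis to section 9 of the protocol and that Table 1.2-1 keeps severity in the endpoint, so the omission looks like a slip. That is probably right, and it limits the seriousness of the point. It does not settle what is to be produced, because the operative list in 2.8.1 lacks the row.

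On dates, several counter-arguments stand. Dates with a known year are imputed, and in the uncertain same-year cells the convention leans towards emergence. The protocol has no rule that is breached. The AE form asks for dates and the data are queried. The SAP nowhere says outright that an AE of unknown year is non-emergent; that follows from the word covering the remainder. A reader might infer that every incompletely dated AE drops out of the tables. The documents support this only when the year is missing.

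On the liver, a reader might infer three stronger things:

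- *That the SAP substitutes neutropenia and candida for the protocol's liver events.* It names its own list and nowhere withdraws the liver events, and protocol 9.5.2 asks for no liver-event table. The reporting duties in protocol 7.3 and Appendix 2 run from site or laboratory to sponsor.
- *That the SAP laboratory limits are wrong.* They match Appendix 1.
- *That the higher liver tiers appear in no output.* They enter through the SAE summaries.

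None of the three is supported.

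**Conclusion.** The severity point holds in full. One category required by protocol 9.5.2 is missing from the SAP, the change is undeclared, and as a result one of the two AE attributes named in the SAP's own endpoint (frequency and severity) is not summarised.

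The date point holds narrowly. It covers only AEs with no start year, and it rests on reading the default in 2.8.1 literally. The emergent tables would be short by the number of such AEs that arose on treatment. The documents do not give that number; it is probably small and could be zero, in which case the rule has no effect. The second definition of emergence in 2.8.1 adds doubt about which rule a programmer should apply.

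The liver point is a recommendation for a low-cost addition and not a departure from the protocol. Only the grouping by Table 14-1 category is missing.

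**What to change.** 1. In SAP 2.8.1, restore the number and percentage of patients with severe AEs, by cohort and overall, for core, extension and the whole study. If the omission was intended, declare it in section 4 and align Table 1.2-1.
2. In SAP 5.1.1, state that an AE with a missing start year counts as treatment-emergent unless its end date is before first dose, and say to which phase it is assigned. In 2.8.1, keep one definition of emergence and make the other agree with it, including the upper limit of the window and the treatment of worsening events.
3. As an addition, summarise liver events by cohort and phase according to the Table 14-1 categories, with potential Hy's law cases shown separately.

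The cost is one row in a planned table, a few sentences of SAP wording and one further table. Severity, AE dates, laboratory values and liver-event pages are all collected already, so no new data are needed.

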2.8.2 Deaths

Deaths will be separately summarized (if there are sufficient number of deaths) by cohorts and overall on the safety set. Also, listing of deaths will be provided on safety set and with relative days from first secukinumab dose.

2.8.3 Laboratory data

Summary statistics of laboratory data and absolute and changes from baseline will be provided by visit and cohort. Summaries will be provided on the following laboratory test and their parameters;

Hematology: Hemoglobin, hematocrit, red blood cell count, white blood cell count with differential (e.g. neutrophils, basophils, eosinophils, monocytes, lymphocytes) and platelet count.

Chemistry: Albumin, alkaline phosphatase, total bilirubin, bicarbonate/CO2, calcium, cholesterol, chloride, creatinine, CK, GGT, glucose, LDH, inorganic phosphorus, lipase, amylase, magnesium, potassium, total protein, AST, ALT, sodium, triglycerides, urea/BUN and uric acid.

Urinalysis: Specific gravity, pH. Summary table of change from baseline will not be perfomed for specific gravity, since the data captured by sites are in different ranges, which cannot be converted.

hsCRP

Patients with values above (H) or below (L) notable criteria (Table 2.8.3) will be listed and absolute and relative frequencies will be presented by visit and cohort. Laboratory values will be presented for each patient in a data listing with an indication of whether the value is above (H) or below (L) the normal reference range.

Laboratory data will also be summarized by presenting shift tables for each laboratory parameter showing the number and percentage of patients in each cohort with the most extreme post-baseline value that falls outside normal ranges by the classification of value at baseline (H/N/L).

For urinalysis of categorical variables (Glucose, Protein, Blood, WBC, RBC), summary table of number and percentage of patients by cohort and visit will be presented.

Laboratory parameter	Criterion for notable abnormalities
Liver Function and Relat	ted Variables
ALT (SGPT)	> 3 x Upper Limit of Normal (ULN)
AST (SGOT)	> 3 x ULN
Total bilirubin	> 2 x ULN

Table 2.8.3 Clinically notable laboratory abnormalities

Alkaline phosphatase (ALP)	> 2.5 x ULN
Renal Function and Elec	trolyte Variables
Serum Creatinine	> 1.5 x ULN
Potassium	> 6 mmol/L or < 3 mmol/L
Sodium	> 160 mmol/L or < 115 mmol/L
Hematology Variables	
Hemoglobin	\geq 20 g/dL decrease from baseline
Platelet count	< Lower Limit of Normal (LLN)
White blood cell count	< 0.8 x LLN
Neutrophils	< 0.9 x LLN
Eosinophils	> 1.1 x ULN
Lymphocytes	> 1.1 x ULN
Urinalysis Variable	
Protein urine dipstick	++* (*++ is > 100 mg/dL)

